## **8 STUDY POPULATION**

The study population will consist of adult male and female renal transplant recipients between the ages of 18-80 years who had received their transplant at least 4 weeks, but not more than 10 years, prior to the screening date. Recipients of any other organ transplant or bone marrow transplant are not eligible. All relevant medical and non-medical conditions should be taken into consideration when deciding whether this protocol is suitable for a particular patient.

### **8.1 Enrollment**

Approximately 60 adult male or female kidney transplant recipients will be enrolled at Vanderbilt University Medical center.

Patients who are willing to participate in the study and who have given written informed consent may be screened up to 7 days prior to enrollment. Screening procedures are detailed in [Section 10.1.1](#).

### **8.2 Eligibility Criteria**

#### **8.2.1 Inclusion Criteria**

1. Patients must be able to understand English and provide written informed consent;
2. Males and females between 18 and 80 years of age;
3. Recipients of a primary or secondary kidney transplant 4 weeks to 10 years prior to screening;
4. Patients receiving a stable dose (i.e., no dose adjustments) of TAC-IR for a minimum of 4-7 days at screening;
5. Patients with a screening TAC-IR trough level of 3-9 ng/mL, measured between Day -7 to 0;
6. Women of childbearing potential must have a negative urine pregnancy test at screening;
7. Patients must be willing to commit to and comply with the schedule of study visits.
8. The patient is not scheduled to begin any new medication that could interfere with tacrolimus blood levels, including prescription and over-the-counter medications, herbal, or food supplements (including grapefruit and pomegranate products), or medications listed in [Appendix 1](#).

#### **8.2.2 Exclusion Criteria**

1. Recipients of any transplanted organ other than kidney;

2. Patients with an estimated glomerular filtration rate (eGFR) (MDRD4) <25 mL/min at screening;
3. Patients with significant visual impairments affecting their ability to complete the study requirements and assessments: patient's vision is 20/200 or worse;
4. Patients with significant hearing impairments affecting their ability to complete the study requirements and assessments, based on Investigator discretion;
5. Patients with any severe medical condition (including infection) requiring acute or chronic treatment that in the Investigator's opinion would interfere with study participation;
6. Patients who have a history of any of the following, based on documentation of clinical conditions and concomitant medications in the medical records:
  - Cognitive decline secondary to stroke
  - Dementia
  - Resected or existing brain tumor
  - Acute or chronic bipolar psychosis or schizophrenia per Investigator discretion
  - Mental retardation
  - Moderate or severe traumatic brain injury
  - Failure of any major organ other than the kidneys (e.g., end-stage liver disease)
  - Known non-adherence (defined as documentation in the patient chart of multiple missed visits and/or medication doses) which in the Investigator's opinion would interfere with the objectives of the study
7. Patients with medical history of hypertension or diabetes which is unmanageable by medically approved intervention (e.g., medication/diet) as assessed by the Investigator;
8. Patients with acute or chronic depression, corresponding to a score of  $\geq 20$  (corresponding to moderate depression) on the BDI-II at screening;
9. Patients who are taking any acute or chronic medications that may impact reaction time, memory, or sleep habits, based on Investigator discretion;
10. Patients on concurrent immunosuppression with MMF (CellCept) or MPS delayed release tablets (Myfortic), or generic versions of these medications, as per SOC, who have not been on stable doses (i.e., no dose adjustments or formulation change) for at least 4-7 days prior to screening;
11. Patients receiving prednisone or equivalent >10 mg/day;
12. Patients with an episode of biopsy-proven or suspected acute rejection that requires treatment within 3 months of screening;

---

 Patients with visual aids (glasses or contact lenses) should be considered, provided their vision is adequately improved with the use of the aid.

 Patients with hearing aids should be considered, provided their hearing is adequately improved with the use of the aid.

13. Patients who are being actively treated for cancer (with the exception of non-invasive basal cell or cutaneous squamous cell carcinoma);
14. Patients known to be human immunodeficiency virus (HIV) positive;
15. Patients with any form of current drug or alcohol abuse as assessed by the Investigator;
16. Patients who were treated with any other investigational agent within 1 month prior to screening;
17. Pregnant or nursing women or women planning to become pregnant, where pregnancy is defined as a state of the female patient after conception and until the termination of gestation, confirmed by a positive urine laboratory test; women of child-bearing potential, defined as all women physiologically capable of becoming pregnant who are unwilling to use a defined SOC birth control method, UNLESS they are:
  - Women whose career, lifestyle, or sexual orientation preclude intercourse with a partner
  - Women whose partners have been sterilized by medically approved means

### **8.2.3 Contraception Guidelines**

ENVARUSUS XR has a pregnancy category C rating. Per the Full Prescribing Information, there are no adequate and well-controlled studies in pregnant women. Tacrolimus is transferred across the placenta. The use of tacrolimus during pregnancy in humans has been associated with neonatal hyperkalemia and renal dysfunction. Tacrolimus given orally to pregnant rabbits at 0.6 times the maximum clinical dose and pregnant rats at 0.9 times the maximum clinical dose was associated with an increased incidence of fetal death *in utero*, fetal malformations (cardiovascular, skeletal, omphalocele, and gallbladder agenesis) and maternal toxicity. ENVARUSUS XR should be used during pregnancy only if the potential benefit to the mother justifies potential risk to the fetus.

As stated in the exclusion criteria, patients of childbearing potential who are unwilling to use a defined SOC birth control unless they are women whose career, lifestyle, or sexual orientation preclude intercourse with a partner and/or whose partners have been sterilized by medically approved means are not eligible to enter the study.

## **8.3 Interruption or Discontinuation of Treatment**

### **8.3.1 Withdrawal from Study**

1. Patients have the right to discontinue study treatment at any time for any reason without penalty or prejudice.
2. The Investigator also has the right to discontinue patients from study treatment if he/she feels it is in the best interest of the patient.
3. A patient may be withdrawn from the study treatment by the Investigator if: (1) the Investigator feels it is not in the patient's best interest to continue in the study, (2) the

patient fails to follow the Investigator's instructions, (3) the patient experiences an adverse reaction that requires other medical treatment, or (4) the patient becomes pregnant.

In the absence of a medical contraindication or significant protocol violation, every effort should be made by the Investigator to keep the patient in the study. Should a patient not complete the study, the patient should complete all the procedures outlined under early withdrawal in the Study Schedule (refer to **Table 3-1**). Reasons for discontinuation will be documented on the case report forms (CRFs).

If, in the opinion of the Investigator, the clinical observations in the study suggest that it may be unwise to continue, the Investigator may suspend or terminate the study.

A written statement will be provided to the Institutional Review Board (IRB) and regulatory authorities, if required.

All patients whose Visit 1 TAC-IR trough level is outside the 3-9 ng/mL range can be rescreened up to 2 times after at least 4-7 additional days on stable dose of TAC-IR.

#### Procedures for discontinuation

If a patient withdraws from the study for any reason all early termination procedures should be completed. Reason for withdrawal, date of discontinuation, and date of the last dose of study medication ENVARSUS XR should be recorded in the study termination section of the CRF. The Investigator is to complete, sign and date the study termination page on the CRF upon completion of the termination visit.

At the time of discontinuation, every effort should be made to ensure that all procedures and evaluations scheduled for the early withdrawal visit are performed. Except in the case of a medical emergency, the following will be performed upon the discontinuation of the study:

- AE assessment
- Review of concomitant medications and ENVARSUS XR

#### 8.3.2 Interruption of Therapy with a Study Drug (ENVARSUS XR)

Patients who require interruption of immunosuppressive therapy for clinical cause anytime between Visit 2 and 3 will be required to be on a stable dose of ENVARSUS XR for a minimum of 4 days before Visit 3 assessments are performed.

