**Drugs Used in Study:**

Each patient will receive the following:

- Investigational product: ENVARSUS XR (tacrolimus extended-release tablets)

ENVARSUS XR tablets will be administered orally q.d. in the morning based on a conversion factor from tacrolimus to ENVARSUS XR of 1:0.8 (see [Appendix 2 or <https://www.envarsusxr.com/hcp/professional-resources/envarsus-xr-dose-converter/> and PI discretion](#)) to maintain target trough level of 3-12 ng/mL. Dose adjustments are not permitted between Visits 2 and 3 unless it is deemed medically necessary at the discretion of the Investigator. If a dose adjustment is required the patient will be required to be on a stable dose of ENVARSUS XR (no dose adjustment) for a minimum of 4 days before Visit 3 assessments are performed (i.e., if a dose adjustment is medically necessary and occurs anytime between Visits 2 and 3 there should be a minimum of 4 days on a stable ENVARSUS XR dose before the Visit 3 assessments take place).

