### **Analysis Sets:**

*Intent-to-Treat (ITT) Dataset:* Includes all patients who are enrolled. The efficacy analyses will be performed using this dataset.

*Evaluable Dataset:* Includes all patients who are enrolled and received at least one dose of ENVARSUS XR and within targeted trough level of 3-9 ng/mL. In addition, the patients must have baseline and post-conversion evaluation for at least one of the cognitive tests (RBANS, TMT-A/TMT-B) without major protocol violation/deviation that would affect the cognitive measurement. The efficacy analyses will also be performed using this dataset.

*Safety Dataset:* Includes all patients who are enrolled and received at least one dose of ENVARSUS XR. The safety analyses will be performed using this dataset.

Patients whose tacrolimus trough level at Visit 3 (or as measured at other SOC visits between Visit 2 and Visit 3) is outside the tacrolimus suggested target trough level of 3-9 ng/mL will still remain in the study. If a dose adjustment is required, the patient will be required to be on a stable dose of ENVARSUS XR (no dose adjustment) for a minimum of 4 days before Visit 3 assessments are performed (i.e., if a dose adjustment is medically necessary and occurs anytime between Visits 2 and 3 there should be a minimum of 4 days on a stable ENVARSUS XR dose before the Visit 3 assessments can take place). However, they will not be evaluable and will be included in the ITT population.

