## 9.3 Dose Adjustments

Patients who require a TAC-IR dose adjustment as a result of screening assessments are not to be considered stable and cannot enter the study, but may be re-screened up to 2 times after at least 4-7 additional days on stable dose of TAC-IR.

Dose adjustments of ENVARSUS XR are not permitted between Visits 2 and 3 unless it is deemed medically necessary at the discretion of the Investigator. If a dose adjustment is required the patient is required to be on a stable dose of ENVARSUS XR (no dose adjustment) for a minimum of 4 days before Visit 3 assessments are performed (i.e., if a dose adjustment is

medically necessary and occurs anytime between Visits 2 and 3 there should be a minimum of 4 days on a stable ENVARSUS XR dose before the Visit 3 assessments can take place). If multiple dose adjustments are required, the Investigator must first obtain Sponsor approval.

ENVARSUS XR dose adjustments to meet therapeutic range in ENVARSUS XR trough levels are permitted after Visit 3 per SOC. In these cases, ENVARSUS XR trough level should be measured, a safety assessment should be completed, and ENVARSUS XR should be dispensed (if applicable).

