## 2.5 Therapeutic Drug Monitoring

Measure tacrolimus whole blood trough concentrations at least two times on separate days during the first week after initiation of dosing and after any change in dosage, after a change in co-administration of CYP3A inducers and/or inhibitors [see *Drug Interactions (7)*], or after a change in renal or hepatic function. When interpreting measured concentrations, consider that the time to achieve tacrolimus steady state is approximately 7 days after initiating or changing the ENVARSUS XR dose.

Monitor tacrolimus whole blood trough concentrations using a validated assay [e.g., immunoassays or high-performance liquid chromatography with tandem mass spectrometric detection (HPLC/MS/MS)]. The immunosuppressive activity of tacrolimus is mainly due to the parent drug rather than to its metabolites. Immunoassays may react with metabolites as well as the parent drug. Therefore, whole blood tacrolimus trough concentrations obtained with immunoassays may be numerically higher than concentrations obtained with an assay using HPLC/MS/MS. Comparison of the whole blood tacrolimus trough concentrations of patients to those described in the prescribing information and other published literature must be made with knowledge of the assay method(s) employed.

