- b) Day of ENVARSUS XR dosing and PK profiling
- c) Arithmetic means ± S.D.
- d) Median [range]
- e) “*De novo*” refers to immunosuppression starting at the time of transplantation
- f) Starting ENVARSUS XR dose = 0.14 mg/kg/day
- g) Starting ENVARSUS XR dose = 0.17 mg/kg/day. *De novo* kidney transplant patients who received ENVARSUS XR starting dose of 0.17 mg/kg/day achieved higher than recommended target tacrolimus trough concentrations, as high as 57 ng/mL during the first 1 to 2 weeks posttransplant.
- h) Tacrolimus trough concentration before the next dose
- i) After 7 days of stable dosing with ENVARSUS XR
- j) AUC0-24 –to- C24 correlation coefficient (r) at steady state was 0.80 or higher
- k) Conversion to ENVARSUS XR at a mean dose of 80% of the total daily dose of tacrolimus immediate-release resulted in equivalent exposure with a 30% reduction in Cmax.

In *de novo* adult kidney transplant patients, the administration of ENVARSUS XR once daily at a starting dose of

0.14 mg/kg/day results in a tacrolimus systemic exposure (AUC24) on Day 1 post-transplant that is up to 10% lower than that of tacrolimus immediate-release capsules twice daily administered at a starting dose of 0.1 mg/kg/day, while similar tacrolimus trough concentrations (C24) are achieved. As steady state is achieved (typically within 7 days of stable

ENVARSUS XR dosing), the AUC24 of ENVARSUS XR is approximately 15% higher than that of tacrolimus immediate-release capsules, at comparable trough concentrations (C24).

In adult kidney transplant patients  $\geq 6$  months post-transplant switched to ENVARSUS XR at 67% to 80% of the daily dose of tacrolimus immediate-release capsules, the steady state tacrolimus exposures ( $AUC_{24}$ ) and tacrolimus trough concentrations ( $C_{24}$ ) were comparable to the  $AUC_{24}$  and  $C_{24}$  measured prior to the switch. However, the mean  $C_{max}$  estimate was 30% lower and the median  $T_{max}$  was more prolonged (6 hours versus 2 hours) following administration of Envarsus XR as compared to that of tacrolimus immediate-release capsules.

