## Excretion

In a mass balance study of orally administered radiolabeled tacrolimus to 6 healthy subjects, the mean recovery of the radiolabel was  $94.9 \pm 30.7\%$ . Fecal elimination accounted for  $92.6 \pm 30.7\%$  and urinary elimination

accounted for  $2.3 \pm 1.1\%$  of the total radiolabel administered. The elimination half-life based on radioactivity was  $31.9 \pm 10.5$  hours, whereas it was  $48.4 \pm 12.3$  hours based on tacrolimus concentrations. The mean clearance of radiolabel was  $0.226 \pm 0.116$  L/hr/kg and the mean clearance of tacrolimus was  $0.172 \pm 0.088$  L/hr/kg.

The elimination half-life of tacrolimus after oral administration of 2 mg ENVARSUS XR once-daily for 10 days was  $31.0 \pm 8.1$  hours (mean  $\pm$  SD) in 25 healthy subjects.

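### Visit 3 may follow only 4 days of stable ENVARSUS XR after an interruption or dose change, while the appended label gives about 7 days to steady state and PIRS-20 looks back 7 days (minor)

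*Combined protocol and SAP*

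**What the plan says.** Section 8.3.2 deals with patients whose immunosuppression is interrupted for clinical cause between Visits 2 and 3. Such a patient "will be required to be on a stable dose of ENVARSUS XR for a minimum of 4 days before Visit 3 assessments are performed". The same floor applies after a dose adjustment. Section 9.3 requires the patient to be "on a stable dose of ENVARSUS XR (no dose adjustment) for a minimum of 4 days before Visit 3 assessments are performed". The synopsis repeats the rule under Drugs Used in Study ("there should be a minimum of 4 days on a stable ENVARSUS XR dose before the Visit 3 assessments take place") and under Analysis Sets ("there should be a minimum of 4 days on a stable ENVARSUS XR dose before the Visit 3 assessments can take place"). No section explains the choice of four days.

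The label reproduced in Appendix 3 uses a longer period. Its Section 2.5 advises that "the time to achieve tacrolimus steady state is approximately 7 days after initiating or changing the ENVARSUS XR dose". In its Section 12.3, the Table 9 profiles in patients at least 6 months after transplant were taken "After 7 days of stable dosing with ENVARSUS XR". Under Excretion, "The elimination half-life of tacrolimus after oral administration of 2 mg ENVARSUS XR once-daily for 10 days was" 31.0 ± 8.1 hours.

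Section 10.2.2.4 gives PIRS-20 a 7-day recall period, and Section 6.2.2 makes its change from Visit 2 to Visit 3 a secondary endpoint. Under the synopsis Analysis Sets, a trough outside 3-9 ng/mL at Visit 3, or "as measured at other SOC visits between Visit 2 and Visit 3", makes a patient non-evaluable, though the patient stays in the ITT set.

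**The concern.** The purpose of a stability rule before Visit 3 is that the assessments there describe the patient on established ENVARSUS XR. Four days falls short of that on two counts. It is shorter than the time to steady state in the protocol's own appendix, and shorter than the recall period of an endpoint scored at that visit.

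The case that matters is a restart after an interruption. On day 4 the PIRS-20 score can still cover days without drug, and the trough drawn that morning is still climbing. The trough also feeds the evaluability rule, with its floor of 3 ng/mL. Nothing reliably removes the affected score: the sentence that makes patients non-evaluable is written for out-of-range troughs and dose adjustments and does not mention interruptions, and the ITT analysis keeps everyone.

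A plain dose change is a much weaker case, because the earlier recall days were still spent on ENVARSUS XR.

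**Working it through.** **Inputs.** Four-day floor: Sections 8.3.2 and 9.3, and the synopsis. Half-life 31.0 h, SD 8.1 h: label Section 12.3, Excretion. Recall of 7 days: Section 10.2.2.4. Enrolment of 60: Section 14.1. Visit 3 at Month 4 ± 30 days, taken as 90 to 150 days. Assumed, because the documents do not give them: length of interruption (1 to 3 days), size of dose change, and share of patients with an event. Kinetics are taken as linear with mono-exponential decay.

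**1. The label's 7 days.** Five half-lives are 5 × 31.0 = 155 h, or 6.5 days. The share of the change still to come after d days is 2^(−24d/31.0). On day 7 this is 0.023, so 97.7% is complete, and the label's figure reproduces. On day 4 it is 0.117, so 88.3% is complete.

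**2. PIRS-20 recall after an interruption.** With k days off drug and testing on day d after restart, off-drug recall days = min(k, 7 − d). The maximum is 3 of 7 on day 4, 2 on day 5, 1 on day 6 and 0 on day 7. This is counting and needs no kinetic assumption.

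**3. Trough after an interruption.** Shortfall = (1 − 2^(−24k/t½)) × 2^(−24d/t½). For k = 2, d = 4, t½ = 31.0 h: (1 − 0.342) × 0.117 = 7.7%.

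| Half-life | Days off drug | Low on day 4 | Low on day 7 |
|---|---|---|---|
| 31.0 h | 1 | 4.9% | 1.0% |
| 31.0 h | 2 | 7.7% | 1.5% |
| 31.0 h | 3 | 9.4% | 1.9% |
| 22.9 h (mean − 1 SD) | 2 to 3 | 4.2% to 4.9% | 0.5% to 0.6% |
| 39.1 h (mean + 1 SD) | 2 to 3 | 10.4% to 13.2% | 2.9% to 3.7% |

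At the evaluability floor, a patient whose steady-state trough is below 3.0/(1 − 0.077) = 3.25 to 3.0/(1 − 0.094) = 3.31 ng/mL would read under 3 on day 4 after 2 to 3 days off drug. By day 7 that limit falls to about 3.05 to 3.06.

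**4. Trough after a dose change.** For new dose/old dose = r, error = ((1 − r)/r) × residual. On day 4, a 20% cut gives 0.25 × 0.117 = +2.9% and a 25% increase gives −0.20 × 0.117 = −2.3%. On day 7 these are +0.6% and −0.5%.

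**5. Patients affected.** With a share p having one event spread evenly over T days, and m days of exposure to the problem, affected = 60 × p × m/T.

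- m = 3 (event 4 to 6 days before a planned visit): 60 × 0.2 × 3/150 = 0.24 to 60 × 0.5 × 3/90 = 1.0.
- m = 7 (every postponed visit rebooked before day 7): 60 × 0.2 × 7/150 = 0.56 to 60 × 0.5 × 7/90 = 2.33.
- Interruptions alone, per 10% of patients interrupted: 60 × 0.1 × 3/150 = 0.12 to 60 × 0.1 × 7/90 = 0.47.

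**The case against.** The strongest objection is size. Even if all 0.47 patients (per 10% interrupted) were tested on day 4 after at least 3 days off drug, off-drug days would be 0.47/60 × 3/7 = 0.34% of the group's PIRS-20 recall days. The trough shortfall, applied to the label's mean of 7.0 ng/mL, is about 0.3 to 0.7 ng/mL, against a between-patient SD of 2.3. Sections 4.2 and 4.6 themselves regard trough as a poor marker of neurotoxicity. All of this stands, and it is why the point is minor. It does not justify the four days.

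Seven days also does not put the whole recall period at steady state; that would take about 14. This is true, but 7 is the shortest period that matches the label and clears the off-drug days. Going to 14 would delay visits further for little gain.

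The baseline side has its own 4-7 day TAC-IR minimum, and Visits 1 and 2 may be combined, so the two ends of the change score would have different floors. That minimum, however, concerns TAC-IR dose adjustments in patients still taking the drug, which is the weak case. Section 8.3.2 concerns therapy that was stopped. The baseline rule is not questioned here.

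Existing safeguards help: dose changes before Visit 3 need medical necessity, interruptions need clinical cause, stability is confirmed before testing, and the Evaluable set drops major deviations affecting cognitive measurement. They keep the number small but do not reach the PIRS-20 score of a restarted patient whose trough is in range.

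**Conclusion.** The concern holds and is minor. The four-day floor conflicts with the label the protocol appends and with the recall period of a secondary endpoint. What follows is confined almost wholly to patients restarted in the last week before Visit 3, whose sleep score then partly describes time off treatment and whose trough reads somewhat low. The recall count is certain. The trough figures rest on first-order kinetics and a half-life measured in 25 healthy subjects. The number of patients rests on event rates that the documents do not supply, so the overall effect cannot be fixed. No change to the sample size is implied.

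**What to change.** Change the minimum from 4 to 7 days before Visit 3 assessments wherever it appears: once in Section 8.3.2, and twice each in Section 9.3, synopsis Drugs Used in Study and synopsis Analysis Sets, seven places in all. Using one number for interruptions and dose changes avoids two competing rules. Leave the evaluability rule as written, including the troughs at standard-of-care visits.

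The cost is that a few Visit 3 dates, with their trough draw, move by up to 3 days. That fits the ±30 days of Table 10-1 and also the +7 days of Section 10.1.7. Section 14.3.2 uses nominal visits without an analysis window, so the shift itself discards no data. Two small risks remain. A moved visit may no longer coincide with a standard-of-care visit, in which case its laboratory tests are charged to the study. A postponed visit that is then missed also loses its RBANS value, since missing data are not imputed. Rebooking should therefore be done when the restart or dose change is recorded.
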